2.8 Specific Drug Supply Requirements

Study drugs Zepatier and Ribavirin will be provided by Merck free of charge to all study participants. Grant support from Merck will also cover the expenses of any laboratory testing which is routine and not covered by the participant's health insurance

Study drugs should be provided to investigator by bulk supplies from Merck and investigators pharmacy (Penn Presbyterian Medical Center) will be responsible for filling individual patient containers and labeling the containers . Blinding of study drugs will not be required in this study. Clinical supplies will be packaged and labeled according to policies and procedures of the Pharmacy Department of the University of Pennsylvania Health System

At conclusion of the study or upon drug expiration, the MSD GRS will be responsible for issuing a Drug Disposition Letter to the investigator for US based studies.

The investigator will be responsible for the destruction of the supplies at the study center pursuant to the ICH/GCP Guidelines, local regulations and the investigator's institutional policies. Clinical supplies will be received by Pharmacist [name] (designated person) at the study site, and will be handled and stored safely and properly, and kept in a secured location (Penn Presbyterian Pharmacy) to which only the investigator and [name] have access. Clinical supplies will be dispensed in accordance with the protocol. Accurate records will be kept of

	
the clinical supplies, the amount dispensed to and returned by the patients, and the disposition at the end of the study.


2.9 Adverse Experience Reporting
	
The investigator agrees to follow the requirements for adverse experience reporting outline in the study agreement.
 
In addition to following the study agreement requirements for adverse experience reporting, this study will monitor and address any adverse experience as follows:
 
 1. Patient's adverse events will be recorded at the time of spontaneous reporting during the period of active drug treatment 2. In addition, patients will be queried about adverse events at weeks 4, 8, and 12 and in those cases with extended treatment, at week 16 3. The principal investigator or sub-investigator (physician or clinical pharmacologist) will determine the severity and relationship to study medication(s) of all adverse events. A physician investigator will review, initial, and date the severity of all adverse events and their relationship to study medications when initial assessment of an adverse event is made by the clinical pharmacologist 4. An adverse event is defined as any untoward medical occurrence in a patient administered a pharmaceutical product and which does not necessarily have to have a causal relationship with this treatment. An adverse event can be any unfavorable and unintended sign or lab result, symptom, or disease temporally associated with the use of Zepatier or Ribavirin whether or not considered related to use of these products. Any worsening of a pre-existing condition that is temporally associated with the use of Zepatier or Ribavirin is also an adverse event 5. All adverse events will be recorded from the time the consent form is signed through 14 days following cessation of treatment and at each 4 week evaluation during the active treatment phase on an Adverse Event case report form 6. Although pregnancy and lactation are not considered adverse events, the investigators will report any pregnancy or lactation in any of the treated subjects including the pregnancy of a male subject's female partner that occurs during the trial and for 6


2.13 Protocol Submission for Investigator-Initiated Studies
	
U.S. protocols should be submitted by US investigators directly or through the Global Research Specialist at www.merckiisp.com
 
Non U.S. protocols should be submitted to the MSD office by the investigators.

Study Procedures

Hepatitis C antibody testing is performed routinely as per unit protocol for the clinical care of dialysis patients. These standard of care labs will be reviewed and Hepatitis C antibody positive patients identified. Patients will have a Hepatitis C viral load and genotype performed. Patients who are viral load positive and genotype 1 or 4 will be eligible to participate and approached about the study.

	Visit 0	Visit 1	Visit 2	Visit 3-5	Visit 6
Study week	prescreening	enrollment	1	4,8,12	24
Review HCV Ab results	X				
HCV viral load and genotype	X				
Sign informed consent		X			
NS5a testing		X (genotype1 only)			
LFTs, PT, PTT, INR, Hepatitis B, HIV		X			
Fibroscan or review of liver biopsy		X			
Referral to Hepatology		X (only for patients with cirrhosis)			
Referral to ID		X (only for patients with HIV)			
Review by Transplant Nephrology		X (evaluate potential for transplant, review listing status)			
Apply for Insurance approval		X			
Start study drug			X		
LFTs			X	X	
HCV VL			X	X	X
Hemoglobin			X (only if on Ribavirin)	X (only if on Ribavirin)	
Adverse event assessment				X	
Compliance assessment				X	

Patients who consent to participate will have a NS5A polymorphism checked in order to determine if Ribavirin administration is required. Study drug(s) will be administered as follows:

Genotype	NS5A	Prior treatment	Drug(s)	Duration
1a	no	no	Zepatier	12 weeks
	yes	no	Zepatier + Ribavirin	16 weeks
	no	yes	Zepatier + Ribavirin	12 weeks
1b	n/a	no	Zepatier	12 weeks
	n/a	yes	Zepatier + Ribavirin	12 weeks
4	n/a	no	Zepatier	12 weeks
	n/a	yes	Zepatier + Ribavirin	16 weeks

Subjects will be instructed to take Zepatier + ribavirin at bedtime. Phosphate binders should be taken at least 3 hours before or 3 hours after taking the Zepatier + ribavirin. If a subject misses a dose of Zepatier + ribavirin and it is less than 8 hours before the next dose, the missed dose should be skipped and the normal dosing schedule resumed. Subjects should not double the next dose to compensate for the missed dose.

Subjects may withdraw consent at any time for any reason or be dropped from the trial at the discretion of the investigator should any untoward effect occur.

Subject will be discontinued from treatment for any of following:

- a. Becomes pregnant during trial
- b. Investigator feels it is in best interest of subject to discontinue such as SAE which investigator feels if possibly or probably related to study medication.
- c. Abnormal LFTs develop: if ALT increases to 10x upper limit of normal and persistently remains 10x upper limit of normal. Discontinuation as well if ALT elevation is accompanied by signs or symptoms of liver inflammation or increasing conjugated bilirubin, alkaline phosphatase, or INR.

Role of Clinical Pharmacologist

- a. Confirming all patients meet inclusion and exclusion criteria
- b. Reviewing patient medications to identify medications which prevent participation or which require specific dosage adjustments or monitoring during the study
- c. Ensuring that all baseline studies have been performed and the results are entered into the clinical case record

- d. Schedule and review with PI all ongoing monitoring labs during active treatment
- e. Schedule and review with PI all post treatment monitoring labs
- f. Dispense Zepatier alone or with Ribavirin depending on presence or absence of polymorphism or prior treatment
- g. Monitor study participants for compliance with study medication
- h. Monitor study participants for any adverse events, record such adverse events in the clinical case record and determine with the physician investigators if the study events are drug related
- i. Obtain third-party approval for payment of study drugs

Additional baseline/screening testing:

- a. Hepatitis C genotype testing
- b. Hepatitis C viral RNA load
- c. Liver function tests
- d. Protine (PT), INR, and Partial Thromboplastin Time (PTT)
- e. HIV test: if positive determine if viral load negative on HAART, viral RNA load, and CD4 and T cell count
- f. review liver biopsy (within 24 months of treatment) or Fibroscan (within 12 months of treatment)
- g. History of alcohol use and alcohol testing when relevant
- h. Hepatitis BsAg and HepB core Ab test - if the Hep BsAg or the Hep Bcore ab is positive, then obtain HBV DNA at weeks 4, 8, 12 of therapy and at SVR12 post therapy
 - i. For patients with Hepatitis genotype 1a, additional testing to determine if NS5A mutation is present or absent.
 - j. For patients with a history of intravenous or alcohol abuse, documentation will be needed to demonstrate that a discussion occurred with the patient discussing the risks of substance abuse and that the provider has offered to get substance abuse help for the patient
 - k. Additional baseline/screening testing/information will be obtained if requested by a third-party payer as a requirement for drug approval
 - l. One office visit for all candidate patients with a hepatologist or infectious disease physician with expertise in hepatitis C management before treatment is initiated to review all laboratory and clinical

history data. At this visit, there will be a determination of the fibrosis stage, including the presence or absence of cirrhosis and to guide optimal choice of therapy as well as determine if there is a need for long term cirrhosis management and liver cancer surveillance. Further office visits with this physician will be determined on presence/absence of cirrhosis and otherwise on an as needed basis as determined by the dialysis nephrologist.

m. Treatment of HIV/HCV co-infected patients will need to be done in collaboration with the patients primary HIV provider prior to starting and during HCV therapy to determine if any adjustments to the HIV regimen will need to be undertaken:

(1). Zepatier can be used with antiretroviral drugs which do not have significant interactions with Zepatier : abacavir, emtricitabine, enfuvirtide, lamivudine, raltegravir, dolutegravir, rilpivirine, and tenofovir. Other antiretroviral drugs allowed will be determined based on package insert, consultation with specialty pharmacists, and the HIV treating physician

Source - <http://www.hcvguidelines.org/full-report/unique-patient-populations-patients-hivhcv-coninfection>

Testing/Evaluations During Active Treatment

a. Liver function tests and RNA viral load at week 4 (only in patients with Childs A cirrhosis), 8, and 12 of treatment. For patients on 16 week therapy, LFT also at week 16.

b. In patients who are treated with combination of Zepatier and Ribavirin, hemoglobin monitoring every week during course of treatment

c. Clinical Pharmacology evaluation for compliance and adverse events at week 4, 8, and 12 (and week 16 for patients receiving a 16 week treatment course).

Testing/Evaluation Post Treatment

a. RNA viral load at 12 weeks post treatment

b. Clinical Pharmacology evaluation 12 weeks post treatment for adverse events and determination if a SVR was achieved at 12 weeks post treatment

c. Patients who have a SVR at 12 weeks will be identified in the hemodialysis treatment records as hepatitis C ab positive but hepatitis C viral RNA PCR negative

Basic Info	Personnel	Sponsors	Sites	Protocol	Populations	Procedures	Consent	Risk/Benefit	Confirmation
------------	-----------	----------	-------	----------	-------------	------------	---------	--------------	--------------

Protocol Form - Miscellaneous

[Back to submission activity](#) [Previous](#) [Next](#)

Clinical Trial*

Is this a clinical trial? Please note the following definition:

- Clinical trial is defined as a research study in which one or more human subjects are prospectively assigned to one or more interventions (which may include placebo or other control) to evaluate the effects of the interventions on biomedical or behavioral health-related outcomes. See CFR 45.46.102(b)

Yes

If Yes, please be aware that for each clinical trial conducted or supported by a Federal department or agency, one IRB-approved informed consent form used to enroll subjects must be posted by the awardee or the Federal department or agency component conducting the trial on a publicly available Federal Web site that will be established as a repository for such informed consent forms.

Investigator Initiated Trial*

Is this an investigator initiated trial? Please select "Yes" if ALL the following conditions are met:

- The research is subject to FDA regulations for human subjects research.
- The individual PI both initiates (plans and designs) and conducts an investigation and under whose immediate direction the investigational agent is administered or dispensed. The individual investigator has absolute responsibility and accountability and designs, conducts, monitors, manages the data, prepares reports and oversees all regulatory and ethical matters. See 21 CFR 312.3

Yes

If Yes, please be aware that the investigator may be required to create and manage a record of this trial in <https://clinicaltrials.gov>.

Drugs or Devices*

Yes: Drugs, products or devices are used in accordance with FDA approval.

For studies including IND or IDE's, please provide the number(s) below

IDE Review*

NOTE: For research involving investigational devices, you are required to review the guidance on Managing Research

Device Inventory.

Consult the Penn Manual for Clinical Research:

<https://somapps.med.upenn.edu/pennmanual/secure/pm/investigational-product-management-sites-not-using-investigational-drug-services-ids>

Please check the box Yes if you have reviewed the guidance.

Yes

Research Device Management*

Please indicate how research device(s) will be managed.

Not Applicable (no investigational devices)

Drug, Herbal Product or Other Chemical Element Management *

Please indicate how drugs, herbal products or other chemical entities will be managed.

Not Applicable (no drugs, herbal products or other chemical entities)

Radiation Exposure*

Are research subjects receiving any radiation exposure (e.g. X-rays, CT, Fluoroscopy, DEXA, pQCT, FDG, Tc-99m, etc.) that they would not receive if they were not enrolled in this protocol?

- IF YES, the protocol must be approved by the Radioactive Drug Research Committee. Consult EHRHS web site: www.ehrs.upenn.edu/protocols/radiohuman.html for submission requirements.
- If you have questions, call [contact].

No

Gene Transfer*

Does this research involve gene transfer (including all vectors) to human subjects?

- IF YES, the protocol must be approved by the Institutional Biosafety Committee. Consult EHRHS web site: www.ehrs.upenn.edu/protocols/bio_humans.html for submission requirements
- If you have questions, call [contact].
- The protocol may also require review by the Senior Vice Provost for Research's Human Research Advisory Committee(HRAC). The IRB will notify the PI and study staff if this review is warranted.

No

Human Source Material*

Does this research include collection or use of human source material (i.e., human blood, blood products, tissues or body fluids)?

- IF YES, consult the EHRHS web site: www.ehrs.upenn.edu/programs/bio/bbpathogens.html for information on OSHA Bloodborne Pathogens requirements (training, vaccination, work practices and Exposure Control Plan).
- If you have questions, call [contact].

No

CACTIS and CT Studies*

Does the research involve Center for Advanced Computed Tomography Imaging Services (CACTIS) and CT studies that research subjects would not receive if they were not part of this protocol?

- IF YES, consult CACTIS website: <http://www.uphs.upenn.edu/radiology/research/labs/cactis/> for application requirements

No

CAMRIS and MRI Studies*

Does the research involve Center for Advanced Magnetic Resonance Imaging and Spectroscopy (CAMRIS) and MRI studies that research subjects would not receive if they were not part of this protocol?

- IF YES, consult CAMRIS website: <http://www.med.upenn.edu/cbi/camris-home.html> for application requirements

No

Investigational Agent or Device within the Operating Room*

Does the research project involve the use of an investigational agent or device within the Operating Room?

- IF YES, contact Associate Executive Director, Surgical Services: [contact]

No

Cancer Related research not being conducted by an NCI cooperative group*

Does this protocol involve cancer-related studies in any of the following categories?

Therapeutic, Prevention, Supportive Care, Screening, Early Detection, or Diagnostic, Epidemiologic, Observational, Outcome, Ancillary or Correlative.

For a description of these categories, see http://www.ctsrmc.org/submitting_a_protocol.php.

NCI Cooperative Groups are as follows:

- Alliance for Clinical Trials in Oncology** **NCI Clinical Trials Group (Canadian Cancer Society) (NCCTG)**
- Children's Oncology Group (COG)** **NRG Oncology Group**
- ECOG-ACRIN Cancer Research Group** **Southwest Oncology Group (SWOG)**

- IF YES, the protocol must be submitted to the Cancer Center's Clinical Trials Scientific Review Committee for scientific review and approval prior to obtaining IRB approval. Consult the CTSRMC website: www.ctsrmc.org for application requirements

No

Processing of Materials*

Will the research involve processing (such as over encapsulating, or compounding)?

No

In-House Manufacturing of Materials*

Will the research involve processing (such as over encapsulating, or compounding)?

No

Medical Information Disclosure*

Does the research proposal involve the use and disclosure of research subject's medical information for research purposes?

Yes

Modified research informed consent document that incorporates HIPAA requirements

CTRC Resources*

Does the research involve CTRC resources?

No

Pathology and Laboratory Medicine Resources*

Will samples be collected by hospital phlebotomy and/or processed or analyzed by any of the clinical laboratories of the University of Pennsylvania Health System?

No

Please confirm analysis is being performed at outside contract laboratories OR confirm that no samples are being collected for research purposes.

** If neither of the above options applies to your research, then please change your answer to the above question. Please confirm analysis is being performed at outside contract laboratories OR confirm that no samples are being collected for research purposes.

** If neither of the above options applies to your research, then please change your answer to the above question.

Research Involves Apheresis, Cell Collection, and/or Blood Product Collection*

Does this research involve collection of blood products in the Penn Donor Center and/or the use of apheresis for treatment or collection of cells or other blood components?

No

Research involving blood transfusion or drug infusions*

Will your research involve blood transfusion or infusion of study drug in 3 Ravidin Apheresis Unit for research purposes?

No

Trial in Radiation Oncology

Is this research a prospective trial being done in Radiation Oncology, and if so, has this protocol been approved by the Radiation Oncology Protocol committee?

N/A

Study in Radiation Oncology

Is this research a retrospective study being done in Radiation Oncology, and if so, has this project been reviewed by the Radiation Oncology Clinical Research Group?

N/A

Use of UPHS services*

Does your study require the use of University of Pennsylvania Health System (UPHS) services, tests or procedures*, whether considered routine care or strictly for research purposes? (UPHS includes all Penn hospitals and clinical practices, including the Clinical Care Associates network of community practices).

*Examples of UPHS services/tests/procedures includes the Clinical Translational Research Center (CTRC), laboratory tests, use of the pathology lab, cardiovascular imaging tests or radiology imaging tests (whether being billed via the Service Center or through UPHS), other diagnostic tests & procedures and associated professional services, etc.

If yes, the following is required:

- Completion and submission of a Prospective Reimbursement Analysis (PRA) to the Office of Clinical Research.
 - There are four PRA Templates: Device, Drug, Non-Drug Device, and Non-Interventional. The links are below:
 - http://www.med.upenn.edu/ocrobjects/prod/CMS/PRA/PRA_Template_Device.xls
 - http://www.med.upenn.edu/ocrobjects/prod/CMS/PRA/PRA_Template_Drug.xls
 - http://www.med.upenn.edu/ocrobjects/prod/CMS/PRA/PRA_Template_Non-Drug_Device_Intervention.xls
 - http://www.med.upenn.edu/ocrobjects/prod/CMS/PRA/PRA_Template_Non-Intervention.xls

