	
pharmacists, and the HIV treating physician Source - http://www.hcvguidelines.org/full-report/unique-patient-populations-patients-hivhcv-coninfection
 
(2). In patients who are taking warfarin, Protime and INR values will be obtained weekly during and following the study to determine if there are any alterations in the Protime and INR due to a Zepatier-Warfarin interaction. Any alterations will result in warfarin dosage adjustments to achieve therapeutic anticoagulation as measured by Protime and INR
 
8. . Testing/Evaluations During Active Treatment
 
a. Liver function tests and RNA viral load at week 4 (only in patients with Child’s A cirrhosis), 8, and 12 of treatment. For patients on 16 week therapy, LFT also at week 16.
 
b. In patients who are treated with combination of Zepatier and Ribavirin, hemoglobin monitoring every week during course of treatment
 
c. Clinical Pharmacology evaluation for compliance and adverse events at week 4, 8, and 12 (and week 16 for patients receiving a 16 week treatment course).
 
9.. Testing/Evaluation Post Treatment
 
a. RNA viral load at 12 weeks post treatment
 
b. Clinical Pharmacology evaluation 12 weeks post treatment for adverse events and determination if a SVR was achieved at 12 weeks post treatment
 
c. Patients who have a SVR at 12 weeks will be identified in the hemodialysis treatment records as hepatitis C ab positive but hepatitis C viral RNA PCR negative

2.6 Study Duration
	
It is estimated all subjects will be recruited and complete treatment over a 9 to 12 month period of time

2.7 Statistical Analysis and Sample Size Justification
	
The co-principle investigators [name] and [name] will be responsible for analyzing all data Since this study does not have a control or comparator group, issues of blinding are non-applicable
 
Statistical Methods
 
The planned primary analysis will be the proportion of patients who following treatment have achieved a SVR at 12 weeks following completion of treatment.

[figure not shown]

Secondary analyses will determine (a) proportion of patients for whom third party approval for Zepatier treatment was successfully obtained (b) logistic barriers to getting third party approval (c) adverse events with treatment

The design of this protocol does not require any specific statistical methods to test the hypothesis

Power/Sample Size:

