- Estimated length of time to enroll all subjects and complete the study
- Length of a subject's participation time in study
- Project date of the proposed study

We estimate this study will take no more than 1 year to complete. We have already identified all of the Hepatitis C antibody positive patients in the dialysis unit via routine clinical screening for Hepatitis C performed for standard of care dialysis center protocol. We anticipate study participants will require 9 months to complete the study. We anticipate it will take up to 3 months to obtain all of the necessary laboratory results and insurance approvals to obtain Zepatier. Patients will be treated for 12-16 weeks depending on resistance testing results. We will then follow the patients for 12 weeks after the completion of therapy to prove they have achieved a sustained viral response (SVR) or cure.

Resources necessary for human research protection

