- Describe the follow-up of subjects and identify any procedures that are performed exclusively for research purposes or performed more frequently than would be clinically indicated (eg: additional x-rays)
- You may upload additional documentation using the **Upload** button below

Since this is a real-world study, all procedures and interactions performed are standard of care in the treatment of dialysis patients with Hepatitis C infection. We will review standard of care Hepatitis C antibody results and follow up any positive results with a Hepatitis C viral load and genotype. Patients who are viral load positive with genotype 1 or 4 infection will be approached about study participation during a standard of care dialysis visit. Patients who consent to the study will have LFTs, Hg, PT, PTT, INR, HIV and Hepatitis B testing performed, these are all the standard laboratory testing required to safely initiate Hepatitis C treatment. We will refer all patients to Hepatology for an evaluation of their fibrosis stage (either by biopsy or fibroscan, at the discretion of the hepatologist); patients who have stage 4 fibrosis (ie cirrhosis) will only be treated in consultation with hepatology. Patients who are HIV co-infected will be referred to infectious disease and their treatment will only be undertaken in consultation with ID. Pharmacy will go through the necessary steps to obtain insurance approval for the medications but all medications will be provided by the study sponsor. Patients will be started on the study drug and have standard of care laboratory tests performed to monitor liver function while on the medication (LFTs and Hepatitis C viral load; hemoglobin will be followed in patients on ribavirin). Once the study drug is completed, patients will have a final Hepatitis C viral load checked 12 weeks after the completion of therapy to document a cure.

The following documents are currently attached to this item:

Procedures (studyprocedures.docx) Date uploaded: 02/27/2018 10:27:30 AM

Deception

No

Are you conducting research outside of the United States? *

No

Analysis Plan

- **Note:** If the statistical methods used are described in the detailed protocol, this section may reference the detailed protocol.

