All analyses will be performed using SAS® for Windows statistical software (SAS Institute, Cary, NC) using validated implementations of each application or SAS custom programming. Programs, logs and output will be reviewed for accuracy according to relevant Standard Operating Procedures (SOPs). A full Statistical Analysis Plan will be developed and finalized prior to data base lock. The plan will include a thorough description of the statistical methods to be used to address study objectives. In general, continuous variables will be summarized with number of non-missing observations, mean, standard deviation (SD), median, minimum and maximum displayed. Categorical variables will be summarized as counts and percentages. For further details, please see section 14. 0 statistical methods of full protocol version 2.0 attached.

The planned primary analysis will be the proportion of patients who following treatment have achieved a SVR at 12 weeks following completion of treatment.

Secondary analyses will determine (a) proportion of patients for whom third party approval for Zepatier treatment was successfully obtained (b) logistic barriers to getting third party approval (c) adverse events with treatment

The design of this protocol does not require any specific statistical methods to test the hypothesis

Power/Sample Size:

A sample size to determine adequate statistical power is not applicable to this protocol since there is only one treatment group and the outcome is binary (SVR at 12 weeks achieved or not achieved) . However, the sample size of approximately 30 patients chosen for this study will be adequate to test the hypothesis and meet the objectives of this study

There are no documents attached for this item.

Data confidentiality

Paper-based records will be kept in a secure location and only be accessible to personnel involved in the study. Computer-based files will only be made available to personnel involved in the study through the use of access privileges and passwords. Prior to access to any study-related information, personnel will be required to sign statements agreeing to protect the security and confidentiality of identifiable information. Wherever feasible, identifiers will be removed from study-related information.

Subject Confidentiality

- Methods to shield participants' identity adequately protect participant privacy.

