Protocol Title: Real World Administration of Zepatier (Grazoprevir plus Elbasvir) in Chronic Hemodialysis Patients with Hepatitis C Infection. Strategies for Identification of Candidate Hemodialysis Patients, Obtainment of Insurance Approval, Treatment Guidelines, and Laboratory and Clinical Monitoring During Therapy Directed to Nephrologists

NCT Number: 03365635

IRB Approval Date: August 13, 2018

Document: Statistical Analysis Plan August 18, 2021

Protocol Title: Real World Administration of Zepatier (Grazoprevir plus Elbasvir) in Chronic Hemodialysis Patients with Hepatitis C Infection. Strategies for Identification of Candidate Hemodialysis Patients, Obtainment of Insurance Approval, Treatment Guidelines, and Laboratory and Clinical Monitoring During Therapy Directed to Nephrologists

Statistical Plan: The planned primary analysis will be the proportion of patients who following treatment have achieved a sustained viral remission (SVR) at 12 weeks following completion of treatment. Secondary analyses will determine (a) proportion of patients for whom third party approval for Zepatier treatment was successfully obtained (b) logistic barriers to getting third party approval (c) adverse events with treatment. The design of the protocol does not require any specific statistical methods to test these hypotheses. A sample size to determine adequate statistical power is not applicable to this protocol since there is only one treatment group and the outcome is binary (SVR at 12 weeks achieved or not achieved). The projected sample size of 25 patients chosen for this study will be adequate to test the hypothesis and meet the objectives of his study.

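### For the two 16-week regimens, the visit table's only post-treatment viral load (study week 24) falls about 8 weeks after treatment, not the 12 weeks that the primary endpoint requires

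*Protocol*

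**What the plan says.** The visit table in the Study Procedures section that follows section 2.13 has this heading row: "Study week prescreening enrollment 1 4,8,12 24". Study drug starts at Visit 2 (week 1). Viral load is marked at Visit 2, at Visits 3-5 (weeks 4, 8 and 12) and at Visit 6 (week 24). The table carries notes for genotype, cirrhosis, HIV and ribavirin, but none for length of course.

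The regimen table in the same section, and the drug schedule in section 2.5, give 16 weeks of treatment to two groups: untreated genotype 1a patients who carry an NS5A polymorphism, and previously treated genotype 4 patients. All other listed groups receive 12 weeks.

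Elsewhere the timing runs from the end of treatment:

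- Section 2.5, and the text below the visit table: "RNA viral load at 12 weeks post treatment", with a pharmacology evaluation for "determination if a SVR was achieved at 12 weeks post treatment".
- Study duration: "Patients will be treated for 12-16 weeks depending on resistance testing results", then "We will then follow the patients for 12 weeks after the completion of therapy".
- Procedures (Protocol Form): "patients will have a final Hepatitis C viral load checked 12 weeks after the completion of therapy to document a cure".
- Primary analysis in section 2.7, in Accrual and in Analysis Plan: the proportion who "have achieved a SVR at 12 weeks following completion of treatment".
- SAP: "sustained viral remission (SVR) at 12 weeks following completion of treatment".

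**The concern.** A fixed study week can match a fixed interval after treatment only if every course has the same length. Here courses last 12 or 16 weeks, so one fixed week cannot serve both.

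SVR12 is the only primary analysis. If staff follow the text, it is measured as defined. If they follow the table, the last sample from a 16-week patient is not an SVR12 sample, and what happens next depends on a rule the SAP does not give:

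- If an undetectable week-24 result is recorded as SVR12, a relapse appearing in the following 4 weeks is missed, which would tend to raise the proportion.
- If the result is treated as missing or as a failure, the proportion could stay the same or fall.

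In each case the reported figure would not be the defined endpoint for those patients. The clinical pharmacologist is responsible for scheduling post-treatment laboratory tests, and a visit table is a natural tool for that. The study also intends to publish a protocol for other dialysis units, so an uncorrected schedule could be copied.

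**Working it through.** **Inputs**

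- Visit 6 at study week 24, drug start at week 1: visit table.
- Course length D = 12 or 16 weeks: section 2.5 and the regimen table.
- Required interval of 12 weeks after treatment: section 2.5 and the SAP.
- Sample size 25 (SAP) or about 30 (section 2.7 and Analysis Plan).

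**Timing**

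Interval at Visit 6 = 24 - end of treatment. SVR12 week = end of treatment + 12. The documents do not say whether a course of D weeks ends at study week D or, with drug started at week 1, at week D + 1. Both readings are shown.

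| Course | End of treatment | Interval at week 24 | SVR12 week |
|---|---|---|---|
| 12 weeks | 12 (or 13) | 12 (or 11) | 24 (or 25) |
| 16 weeks | 16 (or 17) | 8 (or 7) | 28 (or 29) |

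The table's week 24 is reproduced for the 12-week courses: 12 + 12 = 24. It is not reproduced for the 16-week courses on either reading. The shortfall is 28 - 24 = 4 weeks, or 29 - 24 = 5. No other viral load in the table can serve, because weeks 1, 4, 8 and 12 are all on treatment for these patients.

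**Weight of one patient**

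1/25 = 4.0 points; 1/30 = 3.3 points. The documents do not give the number of 16-week patients. Assuming 1 to 5, the share with an off-definition result would be 1/25 to 5/25 = 4.0-20.0%, or 1/30 to 5/30 = 3.3-16.7%.

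**One missed relapse, for scale** (Clopper-Pearson 95% intervals)

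| n | Relapse counted | Relapse missed |
|---|---|---|
| 25 | 24/25 = 96.0% (79.6-99.9) | 25/25 = 100% (86.3-100) |
| 30 | 29/30 = 96.7% (82.8-99.9) | 30/30 = 100% (88.4-100) |

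These counts are illustrations, not forecasts. The documents do not say how often relapse first appears between post-treatment weeks 8 and 12, so no expected bias can be computed.

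**Related gap**

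The table's on-treatment visits stop at week 12. The text below it, and section 2.5, call for liver tests and for compliance and adverse-event evaluations at week 16 in 16-week patients. This does not affect the primary endpoint, but it is another place where the table fits only 12-week courses.

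**The case against.** The strongest reply is that the text already settles the matter. Every narrative statement of the timing says 12 weeks after treatment, and Study duration covers both course lengths. The pharmacologist who would schedule the sample is also told in the text to judge SVR 12 weeks after treatment, and reviews those tests with the principal investigator. Bias needs a 16-week patient, staff following the table over the text, and a late relapse; the documents give no frequency for any of these.

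The table is also plainly condensed. It leaves out the weekly hemoglobin checks and the post-treatment adverse-event evaluation that the text requires, so its silence on course length proves little. It probably comes from the procedures file uploaded in February 2018, before the full protocol was uploaded again in July 2018: the text around it asks for a specialist office visit where section 2.5 asks for a record review. The section 2.4 flowchart is not visible and might show the timing correctly.

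Much of this stands. It makes the practical effect probably small, and the range of 1 to 5 patients is only an assumption. It does not remove the conflict: the procedures file is still listed as a current attachment, the table is in the protocol document, and no visible passage says that the text overrides it.

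**Conclusion.** The concern holds. For the two 16-week regimens, the table puts the only post-treatment viral load about 8 weeks after treatment (7 if weeks run from a week-1 start), against the 12 weeks in the text and SAP. Followed as written, the table would give an off-definition primary outcome for each such patient, worth 4.0 points with 25 patients or 3.3 with 30. The direction of any bias depends on how the SAP would classify the early sample, which it does not state. The arithmetic is certain; the effect on the result is not, and is probably small. This should be fixed because it concerns the timing of the only primary endpoint and costs little to correct.

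**What to change.** 1. In the visit table, define Visit 6 as 12 weeks after the last dose for every regimen (about week 24 after a 12-week course, about week 28 after a 16-week course), not as a fixed study week.
2. Reconcile the table with the text on the week-16 evaluations for 16-week courses.
3. As a secondary step, state in the SAP: (a) that SVR12 is timed from the actual last-dose date, with a prespecified window whose early limit is less than 4 weeks before the 12-week point, so that a post-treatment week-8 sample falls outside it; (b) that an undetectable result before the window does not count as SVR12; (c) how a patient with no sample in the window is classified, for example as not achieving SVR12, with a sensitivity analysis that leaves such patients out.

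The SAP is dated August 2021, three years after IRB approval of a study expected to take no more than one year, so follow-up may be over. If so, item 3 can still be applied to the recorded last-dose and sample dates, and the report should say when the rule was set.

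The cost is one table heading, one week-16 entry and about three SAP sentences, which are analysis decisions as well as wording. No regimen changes, and no test is added beyond what the text requires. For 16-week patients the final sample comes about 4 weeks later than the table shows. With the longest lead-in under Study duration (3 months, about 13 weeks), such a patient finishes at 13 + 16 + 12 = 41 weeks. That is about 2 weeks beyond the stated 9 months (39 weeks), if the lead-in counts towards them, and within the one-year limit.
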